3.2.2. Safety Laboratory Evaluations

At Visits 1, 2, 4, 6 and 8 a qualified staff member will collect blood and urine samples for clinical laboratory analysis. At Visit 2 (Week 0) the samples must be collected prior to the first study medication application. The following tests will be performed:

Chemistry Panel

Albumin
 Alkaline phosphatase (ALP)
 Alanine aminotransferase (ALT)
 Amylase
 Aspartate aminotransferase (AST)
 Blood urea nitrogen (BUN)
 Bicarbonate
 Chloride
 Creatinine
 Gamma-GT
 Glucose
 HbA1c
 Lactate dehydrogenase (LDH)
 Lipase
 Potassium
 Sodium
 Total bilirubin
 Total protein
 Uric acid

Complete Blood Count

Hematocrit
 Hemoglobin
 Platelet count
 Red blood cell morphology
 Red blood cell count
 White blood cell count
 White blood cell differential
 % and absolute:
 Basophils
 Eosinophils
 Lymphocytes
 Monocytes
 Neutrophils

Complete Urinalysis

3.2.3. Vital Signs

At Visits 1-8 a qualified staff member will measure each subject's vital signs. At Visit 1 (Week -6) these measurements will be part of the physical examination. The following items will be measured:

- Body temperature
- Pulse rate
- Respiration rate
- Blood pressure (systolic and diastolic) after the subject sits quietly for at least 5 minutes
- Height (at Visit 1, 6 and 8)
- Weight (at Visit 1, 6 and 8)

3.2.4. Physical Examination

At Visit 1 (Week -6) and Visit 6 (Week 8), the investigator or designee will perform a complete physical examination that will include, at a minimum, evaluation of the following body systems and organs:

- Skin (excluding EBS lesions)
- Cardiovascular system
- Respiratory system
- Head, eyes, ears, nose and throat
- Lymph nodes
- Gastrointestinal/Hepatobiliary (specifically assess for the presence of hepatomegaly and splenomegaly)
- Vital signs

3.2.5. Electrocardiogram (ECG) Monitoring

Single 12 lead ECGs will be performed as outlined in the Study Flow Chart using sensitive electrodes ensuring the subject's skin is not harmed from the procedure (e.g. SofTouch™ Electrodes). The ECGs will be performed on subjects in supine position. The following ECG data will be collected:

- Heart rate
- PR interval
- QRS duration
- QT interval
- RR interval
- Overall Interpretation

3.2.6. Pharmacokinetic Variables

Blood draws for population PK analysis will be drawn at protocol specific timepoints.

4. ANALYSIS POPULATIONS

4.1. Intent-to-Treat Population

The Intent-to-Treat (ITT) Population will consist of all randomized subjects who are dispensed study medication. All efficacy analyses will be conducted using the ITT population. Subjects will be included in the treatment group to which they were randomized.

4.2. Safety Population

The Safety Population will consist of all subjects who receive at least one application of study drug. All safety summaries and analyses will be conducted using the Safety Population. Subjects will be included in the treatment group based on the treatment that was received (if different from the subject's randomized treatment assignment).

4.3. Per Protocol Population

The Per Protocol (PP) Population will consist of all ITT subjects with a BSA and IGA of EBS lesions at Week 8 and without a major protocol deviation as defined by International Conference of Harmonisation (ICH) E3 (*Structure and Content of Clinical Study Reports*) that may interfere with the assessment of drug safety, efficacy and overall integrity of the data. Before data are released for statistical analysis, a blinded review of all data will be performed by the Sponsor's clinical team to identify protocol deviations that may potentially affect the results. At this time, it will be determined if patients and/or data should be excluded from the PP Population. The list of subjects or observations to be excluded from the PP Population, along with the reason for exclusion, will be finalized prior to database unblinding.

5. GENERAL CONSIDERATIONS FOR DATA ANALYSIS

Medpace is responsible for the statistical analyses for this trial. The statistical planning and conduct of analyses of the data from this trial will follow the principles defined in relevant ICH-E9 guidelines and Medpace's Biostatistics SOPs. All tables, figures, and listings will be generated with SAS[®] (SAS Institute Inc. Cary, North Carolina, USA) Version 9.3 or higher and printed using a Rich Text Format (RTF) file format.

5.1. Evaluation of Center Effect

Due to the design, objectives, and sample size of the trial, center effects will not be evaluated.

5.2. Assessment Windows

In the descriptive statistics of safety and efficacy endpoints, only measurements from scheduled visits will be used if values are available. If no values from a scheduled visit are available but values from unscheduled visits are available, the values from the unscheduled visit closest to the target date for that visit will be used for the summary statistics. The date of an unscheduled visit will be used to assign the unscheduled visit to the nearest scheduled visit date.

For analysis purposes, if the event date is on or after the first treatment date, the study day is defined as follows:

$$\text{Study Day} = \text{Event date} - \text{First treatment date} + 1$$

Therefore, the day of the first treatment will be Day 1. If the event date is prior to the first treatment date, the addition of 1 will not be included in the calculation; thus, there will be no Day 0.

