9.2.4. Clinical laboratory sampling

At Visits 1, 2, 4, 6 and 8 a qualified staff member will collect blood and urine samples for clinical laboratory analysis. Topical anesthetics may be used during the blood sample collection. If used the topical anesthetics should be reported as a concomitant therapy. Non-fasting blood samples will be collected at all Visits. At Visit 2 (Week 0) the samples must be collected prior to the first study medication application. The following tests will be performed:

Chemistry Panel

Albumin
Alkaline phosphatase (ALP)
Alanine aminotransferase (ALT)
Amylase
Aspartate aminotransferase (AST)
Blood urea nitrogen (BUN)
Bicarbonate
Chloride
Creatinine
Gamma-GT
Glucose

Complete Blood Count

Hematocrit
Hemoglobin
Platelet count
Red blood cell morphology
Red blood cell count
White blood cell count
White blood cell differential
% and absolute:
Basophils
Eosinophils
Lymphocytes

HbA1c	Monocytes
Lactate dehydrogenase (LDH)	Neutrophils
Lipase	
Potassium	
Sodium	Complete Urinalysis
Total bilirubin	
Total protein	
Uric acid	

The results of the clinical laboratory tests will be reported on the laboratory's standard reports. The investigator must review all laboratory reports in a timely manner and note NCR or CR to define the clinical relevance of any result that is outside the normal range for the laboratory. The investigator must date and initial every laboratory report.

The investigator must review the Visit 1 (Week -6) laboratory results for all the measured analytes for each subject prior to Visit 2 (Week 0). The subject must not be randomized at Visit 2 (Week 0) if any of the Visit 1 (Week -6) results are outside normal range for the laboratory AND, in the opinion of the investigator, CR.

The investigator must report all laboratory results that are BOTH outside the normal range for the laboratory AND, in the opinion of the investigator, CR as medical history if found prior to the first study medication treatment or as an AE if found after the first study medication treatment begins.

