8. ANALYSIS OF SAFETY

Safety will be assessed using the Safety Population. The assessment of safety will include adverse events, clinical laboratory assessments, ECGs, physical examinations, and vital signs. The safety analysis will be based primarily on the frequency of new or worsening adverse events, laboratory abnormalities, and serious adverse events (SAEs). Other safety data will be summarized as appropriate.

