8.3. Safety Laboratory Parameters

Clinical laboratory results will be summarized with descriptive statistics by treatment and visit. Change from baseline will also be summarized. Laboratory values will also be listed by visit, within patient.

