8.4. Vital Signs

Vital signs and the change from baseline will be summarized descriptively by treatment and visit. The count and percentage of subjects with abnormal values will be summarized by treatment and visit. Abnormal blood pressure measurements for subjects age 17 and younger will be defined as either systolic or diastolic measurements above the 95th percentile, according to height, sex, and age. Abnormal blood pressure measurements for subjects age 18 and older will consist of either a systolic blood pressure >140mm Hg or a diastolic blood pressure >90mm Hg. Abnormal weight measurements for subjects age 18 and older will be defined as measurements > 300 pounds (>118 kilograms). Abnormal BMI measurements for subjects age 17 and younger will be defined as measurements above the 95th percentile, according to sex and age. Abnormal values will be defined as clinically relevant (CR) or not clinically relevant (NCR) on the eCRFs. Vital sign data will also be listed by visit, within patient.

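### SAP 5.2 keeps unscheduled values out of the by-visit laboratory, vital sign and ECG summaries when a scheduled value exists, and no any-time or worst-value abnormality table makes up for it

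*SAP*

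**What the plan says.** SAP 5.2 applies to all summary tables: "In the descriptive statistics of safety and efficacy endpoints", "only measurements from scheduled visits will be used if values are available". If the scheduled value is missing, "the values from the unscheduled visit closest to the target date for that visit will be used for the summary statistics". Each unscheduled visit is assigned to the scheduled visit nearest in time.

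The safety tables that follow are all organised by visit:

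- SAP 8.3: "Clinical laboratory results will be summarized with descriptive statistics by treatment and visit". Change from baseline is added, and "Laboratory values will also be listed by visit, within patient".
- SAP 8.4: "The count and percentage of subjects with abnormal values will be summarized by treatment and visit". This is the only abnormality count that SAP 8.3 to 8.5 define.
- SAP 8.5: ECG results by treatment and visit, plus a listing.

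SAP 8 states the basis of the safety assessment: "The safety analysis will be based primarily on the frequency of new or worsening adverse events, laboratory abnormalities, and serious adverse events (SAEs"). Protocol 11.2.4 undertakes to summarise by treatment how often significant laboratory abnormalities occur. SAP 8.3 specifies no such table, and SAP Table 2, which records departures from the protocol, does not list its removal.

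**The concern.** Using scheduled values is right for by-visit means, because it stops repeat testing from weighting a mean towards subjects under closer watch. A count of subjects with an abnormality asks a different question: did this subject have an abnormal value at any time after dosing began? A rule that sets aside unscheduled results can only leave that count unchanged or lower it.

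The point matters most for laboratory data. On sampling, the protocol says: "At Visits 1, 2, 4, 6 and 8 a qualified staff member will collect blood and urine samples". The post-baseline draws are therefore at Weeks 4, 8 and 16. Hepatic injury, pancreatitis and jaundice are events of special interest, and Protocol 3.2 foresees extra blood for rechecks. At stake is whether the by-treatment picture of laboratory, vital sign and ECG abnormalities includes every measurement the trial has collected.

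**Working it through.** The plan states no figure here, and the point rests on no rate or sample size. The check follows an unscheduled value through the rules.

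1. **Before the first application.** SAP 6.3 takes the last pre-treatment measurement as baseline, without limiting it to scheduled visits. Such a value can be used.

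2. **After dosing, assigned to a visit that has a scheduled value of the same test.** SAP 5.2 leaves it out of the by-visit summary. Vital signs other than height and weight are due at all eight visits (Protocol 9.2.2), so an unscheduled reading is displaced unless that visit's own reading is missing. The abnormal vital sign counts of SAP 8.4 are by visit and follow the same rule.

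3. **After dosing, assigned to a visit with no value of that test.** Read literally, SAP 5.2 admits it. Laboratory tests are not due at Visits 3, 5 and 7. To illustrate, with visits on their nominal days:
   - A sample on Day 33 is 33 − 29 = 4 days from Visit 4 and 43 − 33 = 10 days from Visit 5. It goes to Visit 4 and is left out if the Visit 4 sample exists.
   - A sample on Day 38 is 38 − 29 = 9 days from Visit 4 and 43 − 38 = 5 days from Visit 5. It goes to Visit 5, where no laboratory sample is due, and could be admitted.

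   Inclusion then depends on the calendar and not on the result.

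4. **After dosing, judged clinically relevant.** Protocol 9.2.4 makes an out-of-range laboratory result of this kind an adverse event. Protocol 10.1 does the same for clinically significant ECG and other examination findings. Neither is limited to scheduled visits. SAP 8.2 tabulates treatment-emergent events by treatment, not by visit, so the finding reaches a table. SAP 3.2.1 ends the treatment-emergent period 30 days after the last application. With the last application near Day 56, that is 56 + 30 = about Day 86, while the study runs to Day 113. Later events that are neither serious nor of special interest are assured only a listing. That limit comes from the treatment-emergent definition, not from SAP 5.2.

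5. **After dosing, judged not clinically relevant.** The value is not an adverse event by this route. If SAP 5.2 leaves it out of the by-visit table, only the listing remains.

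6. **The numerical peak.** An adverse event term carries no measured value. If a subject's highest value is unscheduled and left out under step 2, no summary shows it, even when the event itself is counted under step 4.

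Steps 5 and 6 are the gap. A by-treatment table of worst post-baseline or any-time abnormalities would close it, but SAP 8.3 to 8.5 specify none.

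**The case against.** The strongest reply is that adverse event reporting already does this work. Every clinically relevant finding becomes an adverse event whatever prompted the sample. The events of greatest concern also have 24-hour reporting (Protocol 10.5.1.1), narratives in the study report (Protocol 10.4.3) and summaries of their own (SAP 8.2). If significant in Protocol 11.2.4 means clinically relevant, the adverse event tables hold much of what was promised. In addition, a recheck usually follows an abnormal scheduled value, which stays in the table. The rule then stops a normal repeat from replacing an abnormal result.

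Much of this stands, and it rules out three stronger readings:

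- A reader might infer that unscheduled abnormal values never enter a safety table, or are visible only in a listing. Steps 3 and 4 show otherwise.
- A reader might infer that abnormal findings concentrate in unscheduled samples. The documents give no distribution of abnormal values by type of visit.
- A reader might take the spacing of the laboratory draws as a measure of what the rule discards. Spacing, with an assumed duration and onset, shows how often a transient elevation would fall between draws. Many such elevations would never be sampled, so no analysis rule could recover them.

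The reply does not remove the gap. SAP 8 names laboratory abnormalities as a basis of the safety analysis alongside adverse events, so it treats them as a separate measure. The adverse event route depends on the investigator's relevance judgement and carries no numerical value. Nothing in the SAP says that the adverse event tables replace the summary in Protocol 11.2.4.

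**Conclusion.** The concern holds in a limited form. SAP 5.2 suits by-visit statistics. The defect is that it also governs the only abnormality count in SAP 8.3 to 8.5, and that no table by treatment delivers the laboratory abnormality frequency on which SAP 8 and Protocol 11.2.4 rely. Following the plan as written can undercount abnormalities. What can be confined to listings is unscheduled values judged not clinically relevant and the numerical peaks of unscheduled values.

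The size cannot be stated. It is zero if no subject's worst value is an excluded unscheduled one, and it grows with the number of such subjects, which the documents do not allow one to estimate. The conclusion assumes that clinically relevant findings are reported as adverse events as the protocol requires. Efficacy conclusions are unaffected. This is a worthwhile, inexpensive correction to safety reporting.

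**What to change.** - **SAP 5.2:** keep the scheduled-visit rule for by-visit descriptive statistics, and state that it does not apply to abnormality counts. Say also how an unscheduled value is handled when the nearest visit does not include that test.
- **SAP 8.3, 8.4 and 8.5:** state that abnormality counts by treatment use each subject's worst post-baseline value from all scheduled and unscheduled assessments. For parameters that can be abnormal in either direction, take the lowest and the highest value.
- **Protocol 11.2.4 laboratory summary:** specify it in SAP 8.3 on this basis and state the criterion for an abnormality. The laboratory's normal range and the investigator's relevance grading are already recorded under Protocol 9.2.4.
- **Sampling intensity:** show the number of unscheduled tests per arm beside these counts.

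The cost is SAP wording and one derived record per subject and parameter. No new data are needed and the by-visit means do not change. SAP 1 permits revisions before database lock. The downside is that an arm with more unscheduled sampling has more chances to show an abnormality, which is why the test counts should be displayed.

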5.3. Handling of Dropouts and Missing Data

5.4. Date Values

In cases of incomplete dates (e.g. AE, concomitant medication, and medical history start and/or stop dates), the missing component(s) will be assumed as the most conservative value possible. For example, adverse events with missing start dates will be considered as treatment-emergent unless the partial date excludes that possibility, e.g. the adverse event month is prior to the treatment infusion month. Otherwise, the first day of the month will be used to impute missing start days and January will be used to impute missing start months. If day is missing for an end date, the last day of the month will be imputed.

Date imputation will only be used for computational purposes such as treatment-emergent status, etc. Actual date values, as they appear in the original CRFs, will be presented within the data listings.

5.5. Non-Date Values

Every effort will be made to obtain required data at each scheduled evaluation from all subjects who have been enrolled.

For the primary analysis of the primary efficacy endpoint (proportion of subjects who achieve $\geq 60\%$ reduction in BSA of EBS lesions with the Assessment Area from Baseline to Visit 6/Week 8), subjects whose status at Week 8 is unknown will be defined to be a non-success/non-responder.

For sensitivity analysis of this endpoint, the following analyses will be performed:

1. Subjects with missing values at Week 8 in the Diacerein treatment group will be imputed as a success, while all subjects in the Placebo treatment group will imputed as a non-success.
2. Subjects with missing values at Week 8 in the Diacerein treatment group will be imputed as a non-success, while all subjects in the Placebo treatment group will imputed as a success.
3. Subjects with missing values at Week 8 will be imputed using multiple imputation (MI) under the assumption of missing at random (MAR). Based on the imputed value at Week 8, the subjects will be assigned accordingly as either a success or non-success.

Missing values for the BSA of EBS lesions within the Assessment Area will be imputed using multiple imputation methodology in two steps. Initially, ten datasets will be generated containing imputed values for non-monotone missing values in the original dataset. The variables used to guide this imputation will include the following: treatment group, age group (<8 and ≥ 8 years old), genotype (KRT5/KRT14 and Other), and BSA

of EBS lesions in the Assessment Area at Baseline, Week 1, Week 4, Week 8, and Week 16. In this step it will be assumed that any intermediate missing data points are MAR. In the second step, the remaining monotone missing values will be imputed. The same variables will be used to guide the imputation as in the first step.

For each imputation dataset, the proportion of subjects who achieve success will be analyzed using the Cochran-Mantel-Haenszel test described in Section 7.1 below. A log transformation will be performed to normalize the relative risk estimates and the standard error of the transformed estimate will be obtained from the log-transformed confidence limits for the relative risk estimate. The results from these ten analyses will be combined and then back-transformed to the original log scale. The corresponding relative risk estimate and confidence interval will be presented.

For the key secondary endpoint, the same imputation methods will be employed as with the primary endpoint. No imputation will be performed on the other secondary or exploratory endpoints.

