11.2.1. Missing Data Handling Methods

Missing data imputation will only be applied to the primary efficacy endpoint, the percentage of subjects with success defined as a $\geq 40\%$ reduction in BSA of EBS lesions at Week 16, for analysis with the ITT Population. If a BSA value at Week 16 is missing, the value will be imputed using last observation carried forward (LOCF). Other sensitivity imputations will be used to test the robustness of this imputation method corresponding to a best-case and worst-case scenario. The best-case scenario will involve missing values at Week 16 being imputed as a success, while the worst-case scenario will involve missing

values at Week 16 being imputed as a failure. No missing data imputation will be applied to the secondary efficacy endpoints.

Adverse events with missing start dates will be considered as treatment-emergent unless the partial date excludes that possibility, e.g. the adverse event month is prior to the treatment infusion month. Otherwise, the first day of the month will be used to impute missing start days and January will be used to impute missing start months.

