7.1. Primary Efficacy Analysis

Descriptive summaries of the proportion of subjects who achieve $\geq 60\%$ reduction in BSA of EBS lesions will be presented by treatment group at each visit.

The primary endpoint is the proportion of subjects who achieve $\geq 60\%$ reduction in BSA of EBS lesions from Baseline to Visit 6 (Week 8). Subjects whose status at Visit 6 is unknown will be defined to be nonresponders. The primary analysis will be conducted using the Cochran-Mantel-Haenszel (CMH) test, stratified by genotype (KRT5/KRT15 and Other) and age group (<8 and ≥ 8 years old). Estimated relative risk, associated 95% confidence interval (CI), and p-values will be provided.

At the final analysis, the treatment groups will be compared using a two-sided test at the $\alpha=0.049$ level of significance in order to account for the alpha spent in the Interim Analysis as described in Section 10 below.

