SAP Section	SAP Section	Description of Change	Impacted Protocol (3a) Section
3.1.4. (Amended from version 1.0)	Exploratory endpoints	
Redefined “exploratory endpoints” as follows:
 
 • The percent change in Reference Lesion Surface Area from Baseline to Visit 8 (Week 16). • The proportion of subjects with a reduction in overall pain intensity from Baseline to Visit 6 (Week 8). • The proportion of subjects with a reduction in overall pruritus intensity from Baseline to Visit 6 (Week 8). • The proportion of subjects with a reduction in overall pain intensity from Baseline to Visit 8 (Week 16). • The proportion of subjects with a reduction in overall pruritus intensity from Baseline to Visit 8 (Week 16).” 
Note: “Mobility” outcomes has been removed; expanded exploratory analysis to include pain intensity and intensity of itch from Baseline to Visit 6 (Week 8)
	5.3 Exploratory Endpoints
3.2	Adverse Events	AEs of special interest (AESIs) have been updated to include all gastrointestinal (GI) disorders defined by MedDRA SOC	10.4.3. Adverse Events of Special Interest
4.1.1	Intent-to-Treat Population	Intent-to-Treat Population (ITT) was clarified to include all randomized subjects who are dispensed study medication (per FDA Advice Letter 26-March 2018)	11.1 Analysis Populations
4.1.3	Per Protocol Population	Editorial update to clarify a major protocol deviation as defined by ICH E3 (Structure and Content of Clinical Study Reports) that may interfere with the assessment of drug safety, efficacy and overall integrity of the data.	

Table 2: Summary of Changes and Impact to Protocol (CCP-020-301; 3a) (Continued)

SAP Section	SAP Section	Description of Change	Impacted Protocol (3a) Section
5.3.3	Data imputation	Incorporated guidance from FDA Advice Letter dated 26 March 2018: “Missing data for the placebo arm will be considered as success while missing data for the diacerein arm will be imputed as failure.”	11.2.1 Missing Data Handling Methods
7.1	Primary Efficacy Analysis	Updated: changed to $\geq 60\%$ reduction in BSA and assessment period from Baseline to Visit 6 (Week 8)	11.2.3 Analysis of Efficacy

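### SAP 5.5 best-case and worst-case analyses assign one outcome to every placebo subject, not only to those missing at Week 8

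*SAP*

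**What the plan says.** The primary analysis in SAP 5.5 and 7.1 counts a subject with unknown Week 8 status as a non-responder. SAP 5.5 then lists three sensitivity analyses:

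- **Scenario 1.** Diacerein subjects with a missing Week 8 value become successes, "while all subjects in the Placebo treatment group will imputed as a non-success".
- **Scenario 2.** Diacerein subjects with a missing Week 8 value become non-successes, "while all subjects in the Placebo treatment group will imputed as a success".
- **Scenario 3.** Multiple imputation (MI) under missing at random, for subjects with missing Week 8 values in either arm. The model uses treatment, age group, genotype and the BSA "of EBS lesions in the Assessment Area at Baseline, Week 1, Week 4, Week 8, and Week 16".

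The end of 5.5 extends the approach: "For the key secondary endpoint, the same imputation methods will be employed as with the primary endpoint".

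Two other places show what was meant. The data-imputation row of Table 2 in SAP 12 gives the regulator's advice that the SAP says it incorporated: "Missing data for the placebo arm will be considered as success while missing data for the diacerein arm will be imputed as failure". Protocol 11.2.1, written for the earlier Week 16 endpoint, also confines its extreme cases to missing values, for example "The best-case scenario will involve missing values at Week 16 being imputed as a success".

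**The concern.** In both scenarios the two arms follow different rules. The diacerein rule covers only missing values, while the placebo rule covers the whole arm. Read as written, the placebo count is 0 in scenario 1 and equals the arm size in scenario 2, whatever was observed.

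A best-case or worst-case analysis should equal the primary result when nothing is missing and move away from it as missing values accumulate. These two, as worded, give an extreme answer with complete data. Two of the three planned robustness checks, on both confirmatory endpoints, would then say nothing about missing data. If the programmer corrects the wording silently, the trial departs from its plan without a record, possibly after unblinding.

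**Working it through.** **Inputs.** SAP 2.2 and 11: 1:1 allocation and 80 subjects, so 40 per arm. SAP 7.1: final two-sided alpha of 0.049. SAP 11: rates of 60% and 30%, which belong to the earlier Week 16 endpoint; the SAP says no data exist for the new one. The documents give no expected missing rate, so the counts below are assumptions. Tests are unstratified Pearson chi-square tests without continuity correction, a simplification of the stratified CMH test.

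**The plan's own figure.** No stated figure is in dispute. The 77% power in SAP 11 uses the same inputs and reproduces. The pooled standard error is √(2 × 0.45 × 0.55 / 40) = 0.1112, the unpooled is √((0.24 + 0.21) / 40) = 0.1061, and power = Φ((0.30 − 1.969 × 0.1112) / 0.1061) = 0.777.

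**Literal wording, nothing missing.** Both scenarios should return the primary result.

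| Observed (diacerein v placebo) | Correct p | Scenario 1, literal | Scenario 2, literal |
|---|---|---|---|
| 18/40 v 18/40 | 1.0 | 18 v 0, p = 1.4e-6 | 18 v 40, p = 3.6e-8 |
| 24/40 v 12/40 | 0.007 | 24 v 0, p = 5e-9 | 24 v 40, p = 8e-6 |

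In literal scenario 1, 4/40 diacerein successes already give p = 0.040. The relative risk has a zero denominator (0/40), so it is undefined. In literal scenario 2 diacerein can at best tie; with 22/40 the relative risk is (22/40) / (40/40) = 0.55, however many placebo values are missing.

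**Missing-only wording.** Take 22 and 11 observed successes, with m subjects missing per arm. Scenario 1 compares 22 + m with 11, and scenario 2 compares 22 with 11 + m.

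| m per arm | Scenario 1 p | Scenario 2 p |
|---|---|---|
| 0 | 0.012 | 0.012 |
| 1 | 0.0066 | 0.024 |
| 2 | 0.0034 | 0.043 |
| 3 | 0.0017 | 0.072 |

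Here both start at the primary result and diverge with m. In this example scenario 2 passes 0.049 at three missing per arm, so the correctly worded check is informative at this sample size.

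**Side point: the MI variable list.** Protocol 8.2.5 and 8.2.7 collect Assessment Area BSA at Week 6 and Week 12; neither is in the model. Week 6 is the last scheduled value before the endpoint. A large simulation followed the SAP's two imputation steps, with assumed two-week correlation of 0.7 to 0.9, success rates of 60% v 30%, and dropout after Week 6 driven by Week 6 status. Leaving out Week 6 shifted the treatment difference by −0.7 to +0.5 percentage points at 5% dropout, −1.5 to +1.0 at 12% and −2.2 to +1.5 at 20%. With Week 6 included, or with random dropout, the shift stayed within 0.2 points, which is simulation error.

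**The case against.** The strongest reply is that nobody would program the literal reading. The verb is impute, which presupposes a missing value. The text sits under the heading on dropouts and missing data, scenario 3 is missing-only, and Table 2 states the missing-only rule for scenario 2. An all-zero or all-success placebo arm would stand out in output review. Most of this stands, and it is why the point is a wording error and not a threat to the trial's conclusions. It does not remove the need to correct: no SAP text restates scenario 1, and 5.5 is the text a programmer works from. Protocol 11.2.1 is weaker support than Table 2, because it concerns a different endpoint and applies the same direction in both arms.

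Two further objections are fair. First, SAP 7.1 asks for the estimate ("Estimated relative risk, associated 95% confidence interval (CI), and p-values will be provided") in the primary analysis, and 5.5 writes out relative-risk reporting only for the MI datasets. That scenarios 1 and 2 must also report one is an inference. Second, losing significance at three missing per arm is ordinary behaviour of a correctly worded worst case, not a consequence of the error.

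On the MI model, omitting a collected visit contradicts nothing in the documents. The simulation favours the point: all dropout falls between Weeks 6 and 8, dependence on Week 6 status is steep, and age group and genotype are left out. Even so the effect is small and its sign depends on the assumed mechanism. Adding Week 12 was not simulated, and it cannot help subjects who leave before Week 8 and do not return.

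**Conclusion.** The concern holds. SAP 5.5 is wrong as written in scenarios 1 and 2, and the error carries to the key secondary endpoint. That conclusion rests on the wording alone. The p-values only illustrate it and depend on 40 per arm, unstratified tests, and assumed success and missing counts. On the literal text, two of the three sensitivity analyses are unusable. On the evident intent, they are sound and worth having. The primary non-responder analysis, the alpha allocation and the sample size are untouched. The error would probably be caught, but it should be corrected in the plan. The Week 6 omission is a minor improvement to one sensitivity analysis (at most about 2 points on the treatment difference in the cases simulated) and adds no weight to the main point.

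**What to change.** In SAP 5.5, limit the placebo clause in both scenarios to placebo subjects who have no Week 8 value: non-success in scenario 1, success in scenario 2. Because the key secondary endpoint takes over these methods, the same edit corrects it. SAP 1 requires revisions before database lock, so the change should be made and recorded by then. The cost is two phrases.

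Optionally, add Week 6 Assessment Area BSA to both MI steps, and Week 12 if wanted. When the IGA imputation model is written out, which 5.5 does not yet do, include Week 6 IGA. These values are already collected, so the cost is one or two extra variables in the code.
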